1.5 Clinical Experience with MEDI-573

This study is the first time that MEDI-573 has been given to humans. From the time the study started and until 17 February 2010, 17 subjects have been treated with MEDI-573 at doses [REDACTED] given once every 7 days. To date no dose limiting toxicities (DLTs) have been observed. Treatment emergent AEs observed in at least 2 subjects each (>10% of subjects) have been the following: decreased appetite, fatigue, anemia, diarrhea, abdominal pain, nausea, vomiting, dehydration, pruritis, thrombocytopenia, early satiety, pyrexia, bronchitis, urinary tract infection, aspartate aminotransferase (AST) increased, blood alkaline phosphatase increased, cough and rash. These events range in severity from Grade 1 to 5, AEs considered to be treatment-related have been Grade 1 or 2.

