Based on simulations using data from the cynomolgus monkey, over a one week dosing interval, on average, approximately 50% suppression of IGF-1 and 70% to 80% suppression of IGF-2 are predicted following administration of 0.5 mg/kg/week. The predicted maximum serum concentrations of MEDI-573 at 0.5 mg/kg every week in man should provide approximately an 80- to a 100-fold safety margin relative to the maximum MEDI-573 concentrations observed following administration of the 60 mg/kg/week dose in the toxicology study in cynomolgus monkeys, a dose at which no adverse effects were observed. At a dose of 10 mg/kg/week, 99% suppression of the targets (IGF-1 and IGF-2) is predicted. Assessment of subjects treated in the 5, 10, or 15 mg/kg cohorts showed complete suppression of circulating IGF-1 and IGF-2. Serum concentrations of MEDI-573 for all 3 cohorts were sustained well above 28 µg/mL, a concentration which has been determined in preclinical in vivo antitumor studies to be the EC₉₀ for tumoral IGF-1R pathway suppression. Based on available pharmacodynamic, pharmacokinetic and safety parameters 5 and 15 mg/kg have been selected for further evaluation in the expansion phase. These two doses provide a dose range in which to compare tolerability and biologic effects achieved at the tumor level.

Evaluation of MEDI-573 activity at the tissue level will be performed in the dose-expansion phase by studies of archived human tumor biopsies when available (optional); any biopsies obtained during surgical procedures conducted in the course of routine patient care (optional); and exfoliated cells in urine, bladder washing specimens, and/or circulating tumor cell samples. Biopsies before and after treatment (including biopsy of metastatic deposits) will be required of all subjects in the dose-expansion phase and will be collected at two timepoints; prior to the first treatment of Cycle 1 and after the last dose of Cycle 1 but prior to administration of the first dose of Cycle 2. These samples will be assessed for phosphorylated

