2.4 Overview

Study Design

This is a Phase 1, multicenter, open-label, single-arm, dose-escalation, and dose-expansion study to evaluate the safety, tolerability, and antitumor activity of MEDI-573 in adult subjects with advanced solid tumors refractory to standard therapy or for which no standard therapy

exists. Approximately 10 investigational sites in the USA will participate in this study, with cohorts of 3 to 6 evaluable subjects each receiving 1 of 5 dosage levels of MEDI-573 [REDACTED] every 7 days in the dose-escalation phase of the study (Cohorts 1 through 5). Two additional dose escalation cohorts will evaluate an alternate every-3-week treatment schedule: [REDACTED] Cohort 6 and [REDACTED] Cohort 7, if applicable, administered as [REDACTED] IV infusion on Day 1 of each 21-day cycle. [REDACTED]. Subjects in the dose escalation phase are considered evaluable if they receive 3 doses of MEDI-573 (Cohorts 1 through 5) or 1 dose of MEDI-573 (Cohorts 6 and 7) and are followed for 21 days from the date of first dose (one cycle) or if they discontinue MEDI-573 due to dose-limiting toxicities (DLTs). Non-evaluable subjects will be replaced in the same cohort. A total of 21 to 42 evaluable subjects will be evaluated during the dose-escalation phase. The decision to continue enrollment in Cohort 7 [REDACTED] will be based on the Sponsor's assessment of PK, pharmacodynamic, IM, and safety assessments obtained from subjects' exposure to MEDI-573 at the [REDACTED] Cohort 6. The rules for enrolling in the next higher cohort are described in Section 4.9.

The dose-expansion phase will evaluate PK and pharmacodynamic parameters and determine tumor response in approximately 20 subjects with advanced urothelial carcinoma (eg, bladder cancer). Two cohorts of approximately 10 subjects each will be examined in the dose-expansion phase. Based on the available pharmacodynamic, pharmacokinetic, and safety parameters, [REDACTED] have been selected for further evaluation in the expansion phase of the protocol. Enrollment in the dose-expansion phase can occur simultaneously with Cohorts 6 and 7. Both dose-expansion dose levels were explored in the dose-escalation phase of the study, in which 17 subjects were enrolled. No MTD has been established at doses of MEDI-573 [REDACTED].

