3.5.2 Treatment Regimens

Subjects will be treated in the dose-escalation phase of the study with 1 of 5 dosage levels of MEDI-573 [REDACTED] (Table 3.5.2-1) administered as [REDACTED] IV infusion once every 7 days, on Days 1, 8, and 15 of repeating 21-day cycles (Cohorts 1 through 5). Two additional dose escalation cohorts will evaluate an alternate every-3-week treatment schedule: [REDACTED] Cohort 6 and [REDACTED] Cohort 7, if applicable, administered as [REDACTED] IV infusion on Day 1 of each 21-day cycle. [REDACTED]. The decision to continue enrollment in Cohort 7 [REDACTED] will be based on the Sponsor's assessment of PK, pharmacodynamic, IM, and safety assessments obtained from subjects' exposure to MEDI-573 at the [REDACTED] Cohort 6. The rules for enrolling in the next higher cohort are described in Section 4.9.

The dose-expansion phase will evaluate PK and pharmacodynamic parameters and determine tumor response in approximately 20 subjects with advanced urothelial carcinoma (eg, bladder cancer). Two cohorts of approximately 10 subjects each will be examined in the dose-expansion phase at dose levels [REDACTED] every 7 days. The first 10 subjects enrolled into the dose expansion phase will receive doses of MEDI-573 [REDACTED] every 7 days. The decision to continue enrollment of subjects in the lower [REDACTED] dose-expansion cohort will be based on pharmacodynamic assessments of tissue obtained from subjects pre and post exposure to MEDI-573 at the [REDACTED] dose level. In the event there is insufficient activity at the tissue level in the higher dose expansion cohort, the sponsor may halt dose expansion and no additional subjects will be enrolled into the expansion phase.

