3.5.4 Administration of Investigational Product

All subjects must be weighed (according to institutional practice) prior to each treatment cycle for calculation of MEDI-573 dosing.

MEDI-573 will be administered to subjects on an outpatient basis as follows:

- 1) Before the MEDI-573 infusion is started, epinephrine 1:1,000, dexamethasone 10 mg, and diphenhydramine (50 mg), or another functionally equivalent H1 blocker, for IV administration and resuscitation equipment for the emergency management of an anaphylactic reaction will be available.
- 2) MEDI-573 will be administered as a 60-minute IV infusion once every 7 days (Cohorts 1 through 5 and the dose expansion phase) or as a 90-minute IV infusion once every 21 days (Cohorts 6 and 7). The Investigator or his/her qualified designee will infuse MEDI-573 until the entire dose is delivered over the infusion period. Vital signs (temperature, respiration rate, pulse, and blood pressure) will be measured immediately prior to MEDI-573 infusion, at every 15 minutes (± 5 minutes) during the MEDI-573 infusion, at the completion of the infusion (± 5 minutes) and 30 and 60 minutes (± 5 minutes) after completion of the MEDI-573 infusion and will be captured in the subject's source documents.
- 3) In the event of an infusion-related reaction, the infusion rate of MEDI-573 may be decreased by 50% or interrupted until resolution of the event (up to 4 hours) and re-initiated at 50% of the initial rate until completion of the infusion. Acetaminophen 650 mg and/or an antihistamine (eg, diphenhydramine 50 mg) or equivalent medications per institutional standard may be administered. Alternatively, or in addition, the rate of infusion of MEDI-573 may be diminished at the discretion of the investigator. Any such activities must be recorded appropriately. If the infusion reaction is severe or prolonged, methylprednisolone 100 mg (or the equivalent) should be administered as well. In such subjects who experience an infusion reaction, prophylactic administration of acetaminophen and/or diphenhydramine or the equivalents may be considered for subsequent administration of MEDI-573.
- 4) Subjects will remain at the study site for at least 60 minutes after the MEDI-573 infusion for medical monitoring.

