4.9 Dose Escalation and Dose Expansion

Rules for dose-escalation are as follows:

- 1) Dose-escalation will begin with a single subject in each cohort. If no DLTs (as defined in Section 4.10) are observed in this subject within the first 7 days of administration of MEDI-573, two additional subjects will be enrolled into that cohort and may be dosed immediately.
- 2) If no DLTs are observed in the first 3 subjects treated in the cohort through the first 21 days of administration of MEDI-573, enrollment in the next higher cohort will begin using the same rules described in Item 1.

Note: The decision to continue enrollment into Cohort 7 [REDACTED] will be based on the sponsor's assessment of PK, pharmacodynamic, IM, and safety data.

- 3) If 1 out of 3 subjects within a cohort experiences a DLT during the first 21 days of administration of MEDI-573, that cohort will be expanded to a total of 6 subjects provided no further subject experiences a DLT. If no further subjects experience a DLT through the first 21 days of administration of MEDI-573 in the expanded cohort, dose-escalation will continue in the next higher cohort using the same rules described in Item 1.
- 4) If 2 or more subjects within a cohort experience a DLT within the first 21 days of administration of MEDI-573, then the MTD will be exceeded and no further subjects will be enrolled into that cohort. If this happens, the preceding cohort will be evaluated as the MTD, with three additional subjects if this cohort has not previously been expanded to six subjects. If ≤ 1 of 6 subjects experience a DLT, this cohort shall be declared the MTD.
- 5) The decision to enroll the next higher cohort or to continue enrollment in the current cohort will be jointly made following a meeting or teleconference attended by all investigators, the medical monitor, a MedImmune Patient Safety physician and optional attendance of the therapeutic area head. A representative from clinical operations will document the discussion and decision. Treating investigators will provide a verbal or written summary of treatment including description of any adverse events. If a treating investigator is unable to attend, a written summary of findings will be submitted. A decision will not be reached unless all treating physicians have attended the meeting or teleconference or submitted a written summary. Dose-escalation will not proceed until approved by the Sponsor.

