5.3 Primary Endpoints

The primary objectives of this study are to evaluate the safety and tolerability of MEDI-573 in adult subjects with advanced solid tumors refractory to standard therapy or for which no standard therapy exists and to determine the MTD or OBED of MEDI-573 in this subject population. The OBED will be the dose at which all circulating IGF-1 and IGF-2 ligand is expected to be sequestered by MEDI-573, and will be based on pre-clinical data, PK/pharmacodynamic modeling, and pharmacodynamic analyses of circulating IGFs in representative samples of human blood collected in the dose-escalation phase of the study. All safety endpoints will be summarized descriptively. Adverse events and SAEs will be summarized by cohort, system organ class, severity, and relationship to MEDI-573 through 30 days after the last dose of MEDI-573. For assessment of the MTD, descriptive statistics will be provided to summarize the occurrence of DLTs by cohort.

Determination of the MTD or OBED is described in Section 4.9 and descriptive statistics will be provided to summarize the occurrence of DLTs by cohort.

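### The fallback rule for the MTD names no schedule, so two or more DLTs in every-3-week Cohort 6 could make weekly Cohort 5 the MTD without any weekly toxicity to support it

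*Protocol*

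**What the plan says.** Section 4.9 of the protocol gives one set of 3+3 rules for all escalation cohorts. Under item 4, if two or more subjects in a cohort have a DLT in the first 21 days, "then the MTD will be exceeded and no further subjects will be enrolled into that cohort". The next step is that "the preceding cohort will be evaluated as the MTD, with three additional subjects if this cohort has not previously been expanded to six subjects". If at most one of six subjects then has a DLT, item 4 makes the declaration of that cohort as the MTD mandatory. No schedule is mentioned.

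The cohorts do not share a schedule. Cohorts 1 to 5 are dosed every 7 days, three doses per 21-day cycle. For Cohorts 6 and 7, Section 3.5.2 says: "Two additional dose escalation cohorts will evaluate an alternate every-3-week treatment schedule". Sections 3.5.2 and 5.1 both refer to Section 4.9 for the enrolment rules directly after describing Cohorts 6 and 7. Section 5.3 adds: "Determination of the MTD or OBED is described in Section 4.9".

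On the weekly record, Section 1.5 reports 17 treated subjects up to 17 February 2010 and states: "To date no dose limiting toxicities (DLTs) have been observed". Section 2.4 says: "No MTD has been established at doses of MEDI-573" (the dose that follows is blacked out).

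**The concern.** To call a dose the MTD under a 3+3 design, a higher dose on the same schedule must have been found too toxic. The cohort just before Cohort 6 is Cohort 5, which is on the other schedule. DLTs after one large infusion every 21 days do not show that a dose above Cohort 5 would be too toxic when given weekly. On the weekly data, the correct statement would be that the MTD was not reached at the highest weekly dose tested.

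Determining the MTD or OBED is a primary objective. In this branch the rule would attach an MTD label that the weekly data do not support, and would enrol three more subjects into a cohort whose own results did not call for them.

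**Working it through.** **The plan's own figure.** The stated escalation size of 21 to 42 evaluable subjects reproduces: 7 × 3 = 21 and 7 × 6 = 42. It is not in dispute.

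**Which steps are affected.** Two or more DLTs in Cohort 7 lead back to Cohort 6, which has the same schedule. Among Cohorts 2 to 5 the fallback stays on the weekly schedule. Only the step from Cohort 6 to Cohort 5 crosses schedules.

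**Would Cohort 5 be enlarged?** Item 2 of Section 4.9 requires at least three subjects in each of Cohorts 1 to 4, so 12 in all. Of the 17 weekly subjects, at most 17 − 12 = 5 were in Cohort 5. That is fewer than six, so the three-subject addition applies, assuming nobody was added to Cohort 5 after 17 February 2010.

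**Inputs for the size.** The protocol gives no DLT rate for Cohort 6, so the true rates p are assumed. One reference value is the one-sided 95% upper limit from 0 DLTs in 17 subjects: 1 − 0.05^(1/17) = 0.1616. It pools several weekly doses and is only indirect evidence for Cohort 6.

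**Formulas**, with q = 1 − p:

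- Trigger, two or more DLTs in Cohort 6 under 3+3: 1 − [q³ + 3pq² × q³].
- Declaration, given no earlier DLT in Cohort 5: at most one DLT in three added subjects, q³ + 3pq². This is the same whether Cohort 5 starts with 3, 4 or 5 DLT-free subjects, if the limit of one in six is read as at most one in total.
- Chance that Cohort 5 is labelled the MTD by this route: the product of the two.

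Example at p = 0.10: q³ = 0.729 and 3pq² = 0.243. Trigger = 1 − (0.729 + 0.243 × 0.729) = 1 − 0.9061 = 0.0939. Declaration = 0.729 + 0.243 = 0.972. Product = 0.0912.

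| Assumed rate, same in both cohorts | Trigger | Declaration | Product |
|---|---|---|---|
| 5% | 0.0266 | 0.9927 | 0.0264 |
| 10% | 0.0939 | 0.9720 | 0.0912 |
| 16.16% | 0.2098 | 0.9301 | 0.1951 |
| 20% | 0.2914 | 0.8960 | 0.2611 |
| 30% | 0.5057 | 0.7840 | 0.3965 |

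**Unequal rates, each between 5% and 30%.** The smallest product is 0.0266 × 0.7840 = 0.021 (Cohort 6 at 5%, Cohort 5 at 30%). The largest is 0.5057 × 0.9927 = 0.502 (Cohort 6 at 30%, Cohort 5 at 5%).

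**The case against.** The strongest reply is that the wording is ambiguous, not wrong. The objective speaks of one MTD or OBED for the drug, Cohorts 6 and 7 are described as an alternate schedule, and a reader could take the preceding cohort to mean the one before on the same schedule. That reading is not written, and for Cohort 6 it points to no cohort at all. The protocol separates the schedules elsewhere, for example in evaluability (Section 5.1), dose modification (Section 3.5.5) and PK sampling (Section 3.7.5), but not in item 4. The study flow diagram is not available, so it cannot settle the matter.

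A second reply is that little depends on the label. This largely stands:

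- Cohort 6 would still be recorded as exceeding the MTD, and DLTs are summarised by cohort.
- The OBED route is unaffected.
- The expansion doses are already fixed. Section 1.6 states: "Based on available pharmacodynamic, pharmacokinetic and safety parameters 5 and 15 mg/kg have been selected for further evaluation in the expansion phase". The higher of these, 15 mg/kg weekly, is presumably the Cohort 5 dose, although the dose table is blacked out. Three more subjects at that dose add no new kind of risk.

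The escalation meeting in item 5 and the Safety Monitoring Committee could review the decision. However, item 5 concerns enrolment, the committee makes recommendations, and neither changes the mandatory wording of item 4.

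A third reply is that the percentages are assumption-driven. This is fair. The 17 subjects are those treated, and the number evaluable for DLT is not given. The range for unequal rates depends on the chosen 30% cap: with Cohort 6 at 50% and Cohort 5 at 5%, the product is 0.828 × 0.993 = 0.82. The figures are illustrations, and the logical fault does not depend on them.

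Finally, an SAP could carry the reporting by schedule. It could not govern the enrolment of three more subjects, which item 4 also decides.

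**Conclusion.** The concern holds, as a minor point. As written, item 4 would evaluate a weekly cohort as the MTD because of toxicity on an every-3-week schedule, and would probably declare it so.

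At assumed equal rates of 5% to 10% the outcome has a chance of about 3% to 9%. At the pooled upper limit of 16% it is about 20%. At 20% and 30%, which lie beyond that limit, it is 26% and 40%. Once Cohort 6 triggers the rule, declaration of Cohort 5 has a probability of 78% to 99% over Cohort 5 rates from 30% down to 5%.

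These figures rest on the assumed rates and on Cohort 5 having no DLT and fewer than six subjects when the rule is applied. The statement that no weekly dose has been shown too toxic is supported up to the 17 February 2010 data date. The consequence is an unsupported label on a primary objective and three unnecessary subjects.

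**What to change.** In Section 4.9 item 4, define the preceding cohort as the one before it on the same dosing schedule. Add that if Cohort 6 has two or more DLTs, the every-3-week MTD is reported as below the lowest dose tested on that schedule and the weekly MTD as not reached, and that Cohort 5 is neither enlarged nor declared the MTD for that reason. In Section 5.3, state that the MTD is reported by schedule.

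The cost is amendment wording in two places. No subjects are added, the planned 21 to 42 stands, and three subjects are saved if Cohort 6 is exceeded. If the sponsor also wants an actual every-3-week MTD in that case, a lower every-3-week cohort of three to six subjects would be needed, taking the total to 24 to 48 (21 + 3 and 42 + 6). That is a separate choice which this correction does not require.

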4.10 Definitions of Dose-limiting Toxicities

Dose-limiting toxicities will be graded according to the NCI CTCAE V3.0 and will be assessed during the first cycle of treatment with MEDI-573 (Cycle 1, Day 1 through Cycle 1, Day 21).

A DLT is defined as:

- 1) Any Grade 3 or higher non-hematologic toxicity that occurs during the DLT assessment period where a cause other than the investigational product (such as disease progression or accident) cannot be reasonably justified with the following exceptions:
 - Grade < 4 serum-high glucose (fasting) with duration of < 24 hours.
 - Grade 3 fever (in the absence of neutropenia) defined as > 40.0°C (>104.0°F) that resolves to normal or baseline within 24 hours of treatment and is not considered an SAE; or
 - Grade 3 rigors/chills that respond to optimal therapy.
- 2) Any Grade 3 or higher hematologic toxicity that occurs during the DLT assessment period where a cause other than the investigational product (such as disease progression or accident) cannot be reasonably justified.

5 Statistical Considerations

5.1 Sample Size

For the dose-escalation phase, a minimum of 21 evaluable subjects (3 subjects in Cohorts 1 to 7) will be required if no subject experiences a DLT. Up to a total of 21 additional evaluable subjects may be enrolled if DLTs occur. Subjects are considered evaluable if they receive 3 doses of MEDI-573 (Cohorts 1 through 5) or 1 dose of MEDI-573 (Cohorts 6 and 7) and are followed for 21 days from the date of first dose (1 cycle) or they discontinue MEDI-573 due to dose-limiting toxicities (DLTs). Non-evaluable subjects will be replaced in the same cohort. The decision to continue enrollment in Cohort 7 [REDACTED] will be based on the Sponsor's assessment of PK, pharmacodynamic, IM, and safety

assessments obtained from subjects' exposure to MEDI-573 at [REDACTED]

[REDACTED] Cohort 6 [REDACTED] The rules for enrolling in the next higher cohort are described in Section 4.9.

Two cohorts of approximately 10 subjects each will be examined in the dose-expansion phase [REDACTED] every 7 days. The first 10 subjects enrolled into the dose expansion phase will receive doses of MEDI-573 [REDACTED] every 7 days. The decision to continue enrollment of subjects in the lower [REDACTED] dose expansion cohort will be based on pharmacodynamic assessments of tissue obtained from subjects pre- and post-exposure to MEDI-573 at the [REDACTED] dose level. In the event there is insufficient activity at the tissue level in the higher dose expansion cohort, the sponsor may halt dose expansion and no additional subjects will be enrolled into the expansion phase.

5.2 Analysis Populations

The safety population will include all subjects who receive any MEDI-573.

The evaluable population for MTD will include all subjects who receive at least 1 full cycle of MEDI-573 and complete the safety follow-up through the DLT evaluation period, or experience any DLT.

5.3 Primary Endpoints

The primary objectives of this study are to evaluate the safety and tolerability of MEDI-573 in adult subjects with advanced solid tumors refractory to standard therapy or for which no standard therapy exists and to determine the MTD or OBED of MEDI-573 in this subject population. The OBED will be the dose at which all circulating IGF-1 and IGF-2 ligand is expected to be sequestered by MEDI-573, and will be based on pre-clinical data, PK/pharmacodynamic modeling, and pharmacodynamic analyses of circulating IGFs in representative samples of human blood collected in the dose-escalation phase of the study. All safety endpoints will be summarized descriptively. Adverse events and SAEs will be summarized by cohort, system organ class, severity, and relationship to MEDI-573 through 30 days after the last dose of MEDI-573. For assessment of the MTD, descriptive statistics will be provided to summarize the occurrence of DLTs by cohort.

Determination of the MTD or OBED is described in Section 4.9 and descriptive statistics will be provided to summarize the occurrence of DLTs by cohort.

